We hypothesize that administering a course of steroids to patients with Graves' or Hashimoto's thyroiditis prior to thyroidectomy will result in a less difficult thyroid operation (measured by a previously validated scale) and a lower rate of surgical complications. Furthermore, we hypothesize administering steroids will results in faster improvement in antibody levels, antibody mediated cytokine levels, and health care quality of life as measured by surveys.

Over the past 5 years, our group has performed nearly 350 thyroidectomies for Graves' or Hashimoto's thyroiditis, giving us nearly 70 potential subjects per year. We have extensive qualitative methods experience and ability to collect QoL data from our recent clinical trial on prophylactic central neck dissection for patients with differentiated thyroid cancer. We developed and validated an instrument to quantify the difficulty of thyroid surgery. This project will be a small pilot that is a non-blinded, randomized trial of patients of glucocorticoids in patients about to undergo surgery for autoimmune thyroid disease. The primary aim of this pilot is really feasibility for the definitive trial: determining willingness of participants and clinicians to

enroll, rates of follow up and response to questionnaires, and time needed for recruitment, collection of data and analysis. The specific aims are for the larger, definitive trial, but will be assessed for this small pilot.

These specific aims are:

- **Determine the benefits and safety of preoperatively administered prednisone for patients with autoimmune thyroid disease undergoing thyroidectomy on:**
 - **Difficulty of surgery^{6,10} and rates of surgical complications**
 - **Serum autoantibody levels**
- **Longitudinally assess the impact of surgical treatment on QoL in patients with autoimmune thyroid disease**

Outcomes:

- Primary
 - Thyroid difficulty Scale score
 - Autoantibody levels
 - QoL scores (12 question Short Form Health Survey [SF-12], thyroid-specific quality of life patient-reported outcome measure for benign thyroid disorders [ThyPRO])
- Secondary
 - Ultrasound doppler quantification of blood flow
 - Surgical complications (parathyroid hormone [PTH] level, recurrent laryngeal nerve [RLN] injury)

Research Design and Methods:

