- Study population = 30 patients with autoimmune thyroid conditions referred to the University of Wisconsin endocrine surgery clinic for surgical management. Patients will be invited to join the study after the decision has been made to proceed with thyroidectomy as the clinical treatment of their autoimmune thyroid disease. Once they have decided to proceed with surgery, we will describe the study rationale and the risks and benefits to enrolling. We will explain that patients will be randomized to take steroids for 1 week prior to surgery, in addition to other medications that we give all patients before surgery. If they choose not to enroll in the study, their thyroidectomy will proceed as planned. For the study, 15 patients will be treated with steroids for 1 week prior to surgery, 15 will not receive steroids. Both otherwise receive the current standard of preoperative care. We are doing a stratified randomization in blocks of four within four groups of patients, as determined by category of diagnosis (Graves' vs. Hashimoto's) and BMI (<35 vs >=35). The small block size will allow for equal numbers of control and treatment subjects even if category sizes are small.
 - Inclusion Criteria: Graves' disease or Hashimoto's disease with positive thyroid autoantibodies (Thyroglobulin Antibody [TgAb], Thyroid peroxidase antibody [TPO], Thyroid Stimulating Ig antibody [TSI], and/or Thyrotropin Receptor antibody [TRAb]). This information is found in the patient's medical record which is available at the time of surgical consultation. If a patient has not had antibody levels checked prior (this is rare), we can discuss the trial with the patient and draw the first set of clinical and research labs. If the clinical labs return that antibody levels are negative, we will inform the patient that they are not eligible to participate and will withdraw them from the study and discard the

research serum sample. All patients must first agree to undergo total thyroidectomy for their disease before they are even approached about the trial.

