 - Because surgeons are not blinded, it is possible that their responses for the thyroid difficulty scale will be altered by their knowledge of whether the subject took steroids. The logistics of having the patients leave the surgeons clinic not knowing their group assignment, then having a different researcher assign and provide the medication would be beyond the budget and capabilities of our team for this feasibility trial. We feel the benefits of ease of enrollment and ability to recruit sufficient patients outweigh the possible bias in the thyroid difficulty scale.
- There are no additional collaborating sites – this will all be performed at UW Hospitals and Clinics
- Identify information extracted from medical records – demographics, length of time of disease, lab values related to thyroiditis disease, indications for surgery,

surgical data including blood loss and length of operation, postoperative laboratory values related to thyroiditis.

- We know that glucocorticoids may decrease Immunoglobulin (Ig)G and IgA levels with moderate-to-high dose steroids given over short term. (10-20 percent at one week in rheumatoid arthritis patients)¹³, therefore we intend to collect serum for antibody levels at intervals more frequent than our standard of care.
- **Specimen/data collection, handling, storage**
 - Data will be collected electronically (REDCap) on the Institute for Clinical and Translational Research (ICTR) secure version of the software and on paper. The only data recorded on paper will be the Thyroid difficulty scale and the prednisone compliance survey and these will be stored in the PI's office in a locked file cabinet.
 - All information obtained and associated data files will be confidential and will be kept in a locked file or password protected secure departmental server through the department of surgery (U:). This server is backed up according to standard protocols. All computers used to access this server are password protected. The risk of breach of confidentiality regarding participation in the study outside of the scope of the research will be handled by carefully controlling access to study data only to personnel on the research team.

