 - Confidentiality will be protected further by: (1) using a participant log form that contains only the minimum necessary protected health information (PHI) concerning participants, and storing this log in a locked area when not in use, (2) not sharing PHI with any outside institution, (3) coding data collection forms with a consecutive participant number that is not derived from any participant personal identifiers, and linking that data collection form to the participant log, and (4) storing the participant log, the key linking the code to the PHI, and data collection forms separately.
 - It is highly likely that these measures will result in avoidance of breach of confidentiality outside of the research. In addition, the data to be collected are not sensitive to participants.
- **Study Procedures:**
 - Eligible patients will have a diagnosis of autoimmune thyroiditis, positive auto-antibodies, and an indication or preference for surgical treatment with a total thyroidectomy. This will be a randomized, non-blinded pilot study, and all patients who are eligible will be given the opportunity to participate.
 - Preoperative Testing: All randomized patients will undergo our current standard of care pre-operative testing, which includes a clinic ultrasound and laboratory testing of thyroid function and autoantibody levels. All study patients will be directed to complete the online quality of life surveys (SF-12 and ThyPRO) prior to surgery. Each survey will take approximately 10-20 minutes to complete. Patients randomized to the steroid arm will be given a prescription for prednisone 20 mg daily for 7 days prior to surgery. Patients will be instructed to take the prednisone once a day, in the morning, with food. All patients (steroid or not) will receive our standard instructions for TUMS and saturated iodine (in Graves' disease) if indicated. Our current standard of care for patients with Graves' disease is to take 1-2 drops of saturated iodine solution

twice a day and 1000mg of TUMS three times a day for the 7 days leading up to surgery. There is no consistent regimen for TUMS or saturated iodine for patients with Hashimoto's in our clinic, but it is up to the clinical judgement of the surgeon whether to use these medications on an individual basis. There are no interactions of these medications with prednisone, and administration or non-use of these medications does not exclude anyone from participating in the trial.

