- 2 weeks postoperatively: Patients are all seen in clinic 10-14 days after surgery and calcium and PTH hormone levels are checked as per our standard of care. Research specific labs of antibody levels will be checked for our study patients (15-45 mL, depending on individual antibody profiles of subjects).
- 6 weeks postoperatively: Patients are all given a lab slip to have thyroid stimulating hormone (TSH) and thyroxine (FT4) drawn to check levothyroxine dosing as per our standard of care, as well as checking antibodies to monitor for treatment success. This can be done at a lab of their choosing. Patients will be sent an electronic link to fill out the quality of life surveys (SF-12 and ThyPRO).

- **6 months postoperatively:** Patients have TSH and FT4 drawn again to check levothyroxine dosing as per our standard of care, as well as checking antibodies to monitor for treatment success. Again, this can be drawn at the lab of their choice. Patients will be sent an electronic link to fill out the quality of life surveys (SF-12 and ThyPRO).

Time point	Procedures (all standard of care)	Labs (italics are current standard of care, black are study specific and in the budget)	Surveys (study specific)
Preop clinic visit (2-4 weeks preop)	Ultrasound with color doppler quantification of blood flow, vocal fold ultrasound	Ca, PTH, TSH, FT4, Tg, TgAb, TSI, TPO, TRAB	SF-12, ThyPRO
Day of Surgery	Repeat ultrasound with color doppler	TgAb/TPO/TSI/ TRAB for any that were positive preop	Thyroid difficulty scale (surgeon)
2 weeks postop	Clinical voice assessment, vocal fold ultrasound	Ca, PTH, TgAb/TSI/TPO/TRAB if they were positive	
6 weeks postop	Laryngoscopy if clinically indicated	TSH, FT4, Tg, TgAb/TSI/TPO/TRAB if they were positive	SF-12, ThyPRO
6 months postop		TSH, FT4, TgAb/TSI/TPO/TRAB if they were positive	SF-12, ThyPRO

- **Study Drug:**
 - Rx will be provided to patients randomized to steroid prep group for “Prednisone 20mg tabs. Sig: Seven days before your scheduled surgery, Take 1 tab (20mg) daily in the morning for 7 daysTake with food. Disp: 7 tabs. Refills: none”
 - Patients will fill this at the UW American Center outpatient pharmacy at no charge, no drug accountability procedures are required for this commercially available drug that is being used in the standard of care dosing and route.

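### Autoantibody values at 6 weeks and 6 months may come from any laboratory, and the plan describes no recording of laboratory or assay

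*Combined protocol and SAP*

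**What the plan says.** The Outcomes list of the combined protocol and SAP puts "autoantibody levels" among the primary outcomes. Under Specific Aims/Study Objectives the hypothesis is that "administering steroids will results in faster improvement in antibody levels", so change over time is what matters. The same section says that the pilot's primary aim is feasibility and that the specific aims belong to the later definitive trial.

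Antibodies are measured before surgery and at four later points: day of surgery, 2 weeks, 6 weeks and 6 months. Study Procedures treats them differently:

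- **Pre-operative:** all randomised patients have "laboratory testing of thyroid function and autoantibody levels", and the schedule table places this at the pre-operative clinic visit. For eligibility, antibody status may also come from the "medical record which is available at the time of surgical consultation".
- **Day of surgery and 2 weeks:** research blood is taken at IV placement and research antibody tests are done around the clinic visit. The reason given is that "we intend to collect serum for antibody levels at intervals more frequent than our standard of care".
- **6 weeks:** hormone tests "as well as checking antibodies to monitor for treatment success. This can be done at a lab of their choosing".
- **6 months:** "Again, this can be drawn at the lab of their choice".

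The data to be extracted include "postoperative laboratory values related to thyroiditis", with no mention of the performing laboratory, assay, units or reference range. Statistical Considerations specifies a two-way mixed-model ANOVA on treatment group, with t-tests where suitable. It does not mention the pre-operative value as a covariate or say how values from different assays would be handled.

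**The concern.** The antibody hypothesis is about how fast a patient's level falls, so each late value has to be read against that patient's earlier one. If the two come from different assays, the difference mixes a biological change with a change of measuring instrument. Two of the four post-baseline measurements are open to this.

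Three things are at stake, all modest. The late between-arm comparison becomes noisier. An antibody SD carried into the next trial's sample size would combine patient and laboratory variation without saying so. And the pilot would not report how often late samples go to another laboratory, which is practical information a feasibility study is well placed to collect.

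**Working it through.** **Reading check.** The plan gives no antibody SD, effect size or power, and 30 patients is justified by recruitment, so there is no stated figure to reproduce. No section describes a central laboratory, shipping of samples, a common assay or conversion of units. The 6-week wording says the check may be *done* elsewhere. The 6-month wording says *drawn*, which could mean local collection only, but no central testing is described.

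**Illustration of size (all variance inputs assumed).** Let
- S = SD of a patient's log change when both values come from the same laboratory, 0.3 to 1.0;
- L = SD of an outside laboratory's log offset from the site laboratory, 0.2 to 0.5;
- p = share of patients whose late value comes from another laboratory, 25% or 50%.

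Pre-operative samples are taken to be run at the site. If each switching patient uses a different laboratory, the variance of late change is multiplied by 1 + p(L/S)².

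| S | p = 0.25, L = 0.2 | p = 0.25, L = 0.5 | p = 0.5, L = 0.2 | p = 0.5, L = 0.5 |
|---|---|---|---|---|
| 1.0 | 1.01 | 1.06 | 1.02 | 1.13 |
| 0.5 | 1.04 | 1.25 | 1.08 | 1.50 |
| 0.3 | 1.11 | 1.69 | 1.22 | 2.39 |

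For example, 1 + 0.5 × (0.5/1.0)² = 1.125. If all switchers share one outside laboratory, the multiplier is 1 + p(1−p)(L/S)², which runs from 1.01 to 1.69 at p = 0.5 and from 1.01 to 1.52 at p = 0.25.

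The largest entry, 2.39, needs L = 0.5 with S = 0.3, that is, laboratories differing by more than patients' own changes vary. If L is instead read as the spread among laboratories with the site as one of them, that corner becomes 1 + [p + p(1−p)](L/S)² = 1 + 0.75 × 2.78 = 3.08. The result depends heavily on L/S, which the documents do not supply.

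**Effect on precision.** The 95% CI half-width for the arm difference in log change is t × SD × √(2/n), with n per arm. Each antibody has at most 15 per arm, because only antibodies positive before surgery are repeated; 8 per arm is an assumed lower case. With S = 1.0, L = 0.5 and p = 0.5, the SD multiplier is √1.125 = 1.061:
- n = 8 (t = 2.145): 2.145 × 1.0 × 0.5 = 1.07, rising to 1.14;
- n = 15 (t = 2.048): 2.048 × 1.0 × 0.365 = 0.75, rising to 0.79.

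The comparison is already wide without any laboratory effect.

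**How well a same-laboratory SD could be estimated.** The 95% limits, as multiples of the estimate, are √(df/χ²). At 8 per arm, all values give 14 df (0.73 to 1.58). If half switch, 4 per arm remain, giving 6 df (0.64 to 2.20). At 15 per arm, all values give 28 df (0.79 to 1.35). With half switching, about 8 per arm remain, giving 14 df (0.73 to 1.58).

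**The case against.** The strongest reply is that this is a feasibility pilot. Its antibody comparison is exploratory whatever the outcome list calls it, and free choice of laboratory is a sensible convenience that helps follow-up. That stands, and it is why the point is minor and why the remedy leaves patients' choice alone.

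Other parts of the defence also stand. The schedule shows a single pre-operative clinic measurement, so there is an obvious baseline; the medical-record result serves eligibility. REDCap may already hold laboratory fields. For 30 patients at one site, the source laboratory might be recovered later from the records, so it would be too strong to say that same-assay change cannot be identified. A laboratory term in the ANOVA might not be estimable with 30 patients and possibly many laboratories, so its absence is not a fault.

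A reader might infer that the late comparison is biased between arms. The documents do not support this: laboratory choice comes after open-label assignment, but nothing links it to arm. A reader might also infer that the next trial will be badly mis-sized. Statistical Considerations says the pilot data will feed that calculation but does not name the outcome to be used, and large distortions arise only in the extreme corner of the assumed range.

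What remains is that the plan, followed as written, pools late values from possibly different assays and describes neither a record of which is which nor a rule for handling them.

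**Conclusion.** The point holds as a minor, inexpensive improvement. For an outcome listed as primary, half of the post-baseline time points may be measured at any laboratory, with no described common assay and no described record of laboratory or assay. The consequence is extra variance in late within-patient change, not expected bias. Its size is unknown: with half the patients switching, it is 2% to 13% if patients' log change has an SD of 1.0, and larger only if that SD is small beside the laboratory differences. These figures rest on assumed values of S, L and p. Early antibody change is largely protected, because the day-of-surgery and 2-week samples are not left to patient choice, although the laboratory that runs them is not named either.

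**What to change.** - In REDCap, record laboratory, assay, units and reference range for every antibody value, including the pre-operative one. If these fields already exist, or if 6-month samples are to be tested centrally, say so in the protocol.
- Compare arms for each baseline-positive antibody separately, with the pre-operative clinic value as covariate, on the log scale where the assay allows.
- Keep all 6-week and 6-month values in the intention-to-treat analysis. Add a sensitivity analysis limited to values from the same laboratory and assay as the pre-operative sample, and read it as supportive only, because laboratory choice comes after randomisation.
- Report the share of late values from another laboratory as a feasibility result.
- If an antibody SD is used to size the next trial, state whether it is the all-laboratory or the same-laboratory SD, and give its confidence interval.

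The cost is some protocol wording, a few data fields and a little extra data entry, with no added blood draws or visits and no loss of choice for patients. The main limitation is that the same-laboratory SD will be imprecise, so it may not show a small inflation even if one exists.

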- Day of Surgery: Surgeon will repeat the ultrasound in the operating room to compare area of blood flow. As part of the clinical workup, each surgeon always performs thyroid ultrasound using our GE Logiq clinic equipment, and this includes a single image using "doppler" mode to measure blood flow. Surgeons then do an ultrasound once the patient is positioned in the operating room to verify incision placement, and for study patients we will save one "Doppler" image for comparison purposes to the preop image. While the single image is unique to this study, performing the ultrasound is part of our routine clinical care and saving one additional image takes 10 seconds and confers no additional risk. There is no charge for this image and it will be uploaded with the clinical image to the radiology digital storage system for the surgeons to compare blood flow from before and after steroid administration. Research specific blood draw (15mL) will occur at the time of IV placement and sent for antibody levels. Patients will be asked whether they took their course of steroids as described and we will record their answers. If they report not taking it as directed, their narrative reasons for not doing so will be recorded. Total thyroidectomy will be performed using standard techniques in all patients potentially eligible for randomization. An open technique will be used to remove the entire thyroid including pyramidal lobe and all visible thyroid tissue. Care will be taken to visualize and preserve both recurrent laryngeal nerves and to preserve all parathyroids *in situ*. All removed specimens will be carefully examined for any parathyroid tissue and any devascularized or resected normal parathyroid glands will be confirmed by frozen section and autotransplanted into the sternocleidomastoid muscle, as per our standard of care. The surgeon will then fill out the "Thyroid Difficulty Scale" at the conclusion of the operation, either by the surgeon entering it directly into the secure RedCap project or recording their answers on paper that is coded and entered later. If on paper and coded, surgeons will store the paper separately from any PHI related to that subject and will destroy the paper as soon as it is entered into the database.

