 - Concomitant medications allowed/disallowed: No other steroids or immunosuppressive medications, No antibiotics, antitubercular drugs, or anti-fungals. No anticoagulants. Caution in many anti-seizure medications.
 - No placebo
 - While chronic systemic steroids may impair wound healing, there is literature to support that acute (< 10 days), high-dose systemic corticosteroid use has no clinically significant effect on wound healing¹⁴
 - The prednisone dose is within the accepted guidelines for rapid prep for Graves’ disease patients, and is considered a moderate dose. It is expected to contribute negligible increased risk for wound complications in this population where wound infection rates are already extremely low (less than 0.5%).
- **Data and Safety Monitoring Plan:**
 - This is a study that involves randomizing patients to receive a prescription drug, therefore is greater than a minimal risk study. It is using a commonly prescribed medication for a short duration and has been shown to have a low incidence of adverse events at these doses and durations. Prednisone is already prescribed

in a subset of similar patients to our population outside the context of a trial (Graves' disease requiring rapid surgical prep). Potential problems will be monitored and handled by the primary surgeon, clinic staff and principal investigator. This is appropriate given the small number of participants (15 subjects will receive the intervention drug), single site, and low risk medication. We will not assemble a formal *external* Data and Safety monitoring committee..

- [name] will be notified by the enrolling surgeon each time a subject enrolls in the trial and of any protocol deviations. Adverse events from the study medication will be reported immediately. We anticipate that the manner in which subjects will report adverse events is by (1) directly notifying the principal investigator as directed in the informed consent document, (2) calling our clinic staff who will notify [name], or (3) by reporting side effects and amount of drug taken on the drug compliance survey on the day of surgery.
- Protocol violations and deviations, side effects, and adverse events will be noted in the secure RedCap database.
- A monthly clinical research meeting occurs among our group to discuss all clinical research, and this study will become a standing item on our agenda during the duration of the trial for any surgeon to discuss possible adverse events or concerns

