- Given low rates of wound infection in this population, any wound infection requiring treatment with antibiotics in the steroid group will be considered an adverse event (AE) and will be investigated immediately by the principal investigator and operating surgeon, and reported to the IRB within 14 business days. If a wound infection requires an operation, it is considered a serious adverse event (SAE), although it is not immediately life threatening or debilitating to other subjects, so also will be reported with 14 business days to the IRB. If a second wound infection requiring antibiotics or surgery occurs in the steroid treated group, enrollment will immediately cease and it will be reported as a SAE in the same 14 day timeframe, when we will closely scrutinize these cases with the help of the IRB to determine whether it is safe to proceed. Monitoring for wound infections will occur in the context of our usual clinical care. We will see every wound in person at the postoperative visit, but otherwise we rely on patients self-reporting to alert clinic staff if they have concerns (redness, warmth, drainage) about their incisions. No specific study-specific instructions will be given to study subjects, we will simply ask them to call the clinic staff if they have any concerns, and clinic staff will be trained to immediately notify [name] if a study patient reports wound complications.
- Statistical Considerations: Provides an explanation as to why the number of subjects was chosen and the means for analyzing data will meet the specific aims/study objectives
 - As a small pilot, feasibility study, the size of 30 is based on our estimate of a realistic recruitment rate for the future definitive trial. We see approximately 70 potential subjects in our clinics per year, and our listed exclusion criteria are rare in our population. We estimate that fewer than one fourth will not meet criteria, and an additional one fourth may decline to participate. From the patient perspective, enrollment involves only answering QoL surveys and possibly taking a medication 1 week prior to surgery, the risks and effort are not much greater, which is why we estimate a generous rate of inclusion. We are giving ourselves 1 year to enroll all 30 patients (with an additional 6 months to collect follow up data). Our biostatistics team has already been engaged and feels this is an aggressive but realistic expectation. For all primary aims, data will be analyzed

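### Antibiotic-treated wound infection is labelled an adverse event only in the steroid arm, and the one side-effect form appears meant for prednisone takers, so like-for-like control counts are not secured (minor)

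*Combined protocol and SAP*

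**What the plan says.** **Wound infection.** The Data and Safety Monitoring Plan says that "any wound infection requiring treatment with antibiotics in the steroid group will be considered an adverse event (AE"). The next sentence has a different scope: "If a wound infection requires an operation, it is considered a serious adverse event (SAE"), with no arm named. The same paragraph has every wound inspected at the postoperative visit and has clinic staff pass on wound complaints from any study patient. The logging line also names no arm: "Protocol violations and deviations, side effects, and adverse events will be noted in the secure RedCap database".

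**Side effects.** The same section expects adverse events to reach the team by three routes: telling the principal investigator, calling the clinic, or "by reporting side effects and amount of drug taken on the drug compliance survey on the day of surgery". Only the third is a form. The data-handling section calls it by a narrower name: "The only data recorded on paper will be the Thyroid difficulty scale and the prednisone compliance survey". The Day of Surgery procedures describe a question about the steroid course: "Patients will be asked whether they took their course of steroids as described and we will record their answers". The time-point table lists only the surgeon's difficulty scale on the day of surgery and no survey at 2 weeks. The quality-of-life surveys are not repeated until 6 weeks.

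**Background treatment.** Under Preoperative Testing, "All patients (steroid or not) will receive our standard instructions for TUMS and saturated iodine", but the sentence goes on to restrict the iodine to Graves' disease and the instructions to cases where they are indicated. For Graves' disease the standard includes "1000mg of TUMS three times a day for the 7 days leading up to surgery". For Hashimoto's disease the clinic has no consistent regimen.

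**Aim.** The first specific aim names the safety of prednisone as well as its benefits. The items beneath it are difficulty, surgical complications and antibody levels. The listed complications are PTH level and RLN injury.

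**The concern.** The control arm is what allows a symptom or infection after a week of prednisone to be set against background. That works only if both arms are counted in the same way. Here two things differ, or appear to differ, by arm: the label that makes an antibiotic-treated infection an adverse event, and the prompt that elicits side effects.

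The side effects listed under Physical Risks (nausea, gastrointestinal upset, appetite change, mood change, insomnia) are non-specific. Patients awaiting thyroidectomy may have them without prednisone, and some in both arms take calcium tablets, with or without iodine, in the same week. If steroid patients are asked and controls must volunteer, the steroid arm will tend to show more symptoms even when the true rates are equal. The pilot is meant to supply preliminary data for a larger trial, so an artificial excess could be carried forward as a tolerability signal.

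**Working it through.** The plan gives no adverse-event rate, expected count or test for this point, so there is no figure of its own to reproduce. The check is a comparison of the text, followed by illustrative arithmetic.

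**1. Which steps are limited to one arm**

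| Step | Arm named? |
|---|---|
| Adverse-event label, infection treated with antibiotics | Steroid only |
| Serious-event label, infection needing an operation | None |
| Wound inspection and staff notification | None (all study patients) |
| Logging of side effects and adverse events in REDCap | None |
| Contacting the principal investigator or clinic | None |
| Compliance survey on the day of surgery | Not stated; name and content concern prednisone |

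The two parts concern different events. A form completed on the day of surgery cannot capture a postoperative infection, so the survey bears on drug-type symptoms and the label bears on infection.

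**2. Wound infection**

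Inputs from the documents: 15 patients per arm, and a background rate below 0.5%. At 0.5%:

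- Expected infections per arm: 15 × 0.005 = 0.075.
- Chance of at least one in 15: 1 − 0.995^15 = 7.2%.

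**3. Side effects (assumed inputs)**

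The following are assumptions, not figures from the documents:

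- true symptom rate p, equal in both arms, 10-40%;
- proportion s captured when prompted (steroid arm), 100% or 80%;
- proportion c volunteered without a prompt (control arm), 25-75%.

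The true difference is zero, so the bias in the recorded difference is p × (s − c).

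- Full capture, low end: 0.10 × (1 − 0.75) = 2.5 points (0.375 of 15 patients).
- Full capture, high end: 0.40 × (1 − 0.25) = 30 points (4.5 of 15 patients).
- 80% capture, low end: 0.10 × (0.80 − 0.75) = 0.5 points.
- 80% capture, high end: 0.40 × (0.80 − 0.25) = 22 points.

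Mid-case, p = 20% and c = 50%:

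- Full capture: 15 × 0.20 = 3.0 expected reports against 15 × 0.10 = 1.5. The bias is 10 points. The standard error of the difference at 20% in each arm is √(2 × 0.2 × 0.8 / 15) = 14.6 points, so the bias is 0.68 standard errors.
- 80% capture: 15 × 0.16 = 2.4 expected reports against 1.5.

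Exact binomial chance that the steroid count exceeds the control count, p = 20%, 15 per arm:

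| Control symptoms recorded | Full prompted capture | 80% prompted capture |
|---|---|---|
| Same capture as steroid arm | 41% | 40% |
| 75% volunteered | 55% | 43% |
| 50% volunteered | 70% | 58% |
| 25% volunteered | 84% | 76% |

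Each column should be read against its own first row. With 80% capture and 75% volunteered, the shift is only from 40% to 43%.

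A split of 3 of 15 against 1 of 15 gives a two-sided Fisher p of 0.60. The issue is therefore how a descriptive table reads, not the result of a test.

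**The case against.** The strongest reply has four parts.

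- **The wound-infection sentence is a safety trigger.** It ties the label to prompt investigation and IRB reporting, which is reasonable for exposed patients, and need not be the trial's data definition. This largely stands. A reader might infer that control infections go unmonitored or that serious control events go unreported. The documents do not support that, because detection, the serious-event sentence and logging are not limited by arm. What remains is that no sentence gives a control infection treated with antibiotics the same label.
- **Nobody has seen the form.** That it prompts for side effects, and that controls do not receive it, are both inferred. The reporting routes refer to subjects generally. The time-point table cannot settle the matter, because it omits the compliance survey altogether. This stands as a limit on confidence. A reader might infer that controls are excluded from the form, but the text does not say so. It equally never commits to giving it to them.
- **No analysis depends on it.** Side effects and wound infection are not listed outcomes, Statistical Considerations plans no adverse-event comparison, and the protocol describes feasibility as the pilot's real primary aim. This stands. A reader might infer that the future sample size would be distorted, but the documents do not link these data to that calculation.
- **Open-label reporting bias would remain anyway.** True, but unequal prompting is a separate source of bias, and it can be removed.

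**Conclusion.** The point holds as a minor one. The steroid-only label is explicit. The steroid-only form is a reasonable inference from its name and content, held with medium confidence. Together they leave control events without the same definition and prompting, in a randomized study whose first aim includes the safety of prednisone. The likely direction is against prednisone, in any by-arm description of symptoms.

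The symptom part could matter, but its size is illustrative only. It rests wholly on assumed rates and ranges from negligible (0.5 points) to large (30 points). The infection part has almost no numerical weight at the documents' own rate and mainly aligns a definition. PTH and RLN injury are assessed alike in both arms and are not in question. It would go too far to say that the calcium and iodine instructions put every patient on the same background treatment: they apply where indicated, with no consistent Hashimoto's regimen.

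**What to change.** - **Side effects.** On the day of surgery, ask all 30 patients the same short questions, covering the symptoms named under Physical Risks over the preceding 7 days. Keep the adherence items for the steroid arm. Add the form to the time-point table. If the existing survey already goes to everyone with these questions, a sentence saying so closes this part.
- **Wound infection.** Add a sentence such as: A wound infection needing antibiotics or an operation is recorded in REDCap under the same definition in both arms. Leave the existing investigation, IRB-reporting and enrolment-pause wording unchanged.
- **Reporting.** Present both items by randomized arm, descriptively and without a test.

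The cost is one brief checklist for 15 controls who are already present that day, one schedule entry and one or two sentences. With 15 patients per arm the comparison stays descriptive, and because treatment is open-label, expectation can still affect self-reported symptoms.
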